17.0 Data Management and Analysis

17.1 Describe the data analysis plan, including any statistical procedures. This section applies to both quantitative and qualitative analysis.

Study 2:

Data Analyses

For the RCT, data will be analyzed according to the intention-to-treat principle [122]. All participants who complete the baseline assessment will be followed (i.e., post-intervention, 3-month and 6-month post-intervention) regardless of treatment participation. Given our experience and past record of retaining participants in longitudinal studies and the relatively brief period of follow-up (6-mos), dropout due to attrition is expected to be low. We anticipate no more than 5% of data will be missing through attrition or wave nonresponse (i.e., not completing all measures at a given time period). To adjust for any missing assessments, we will use multiple imputation procedures [123, 124].

We have three specific hypotheses for the RCT, our analyses are organized below for each hypothesis.

Hypothesis a: Participants in the RPCW intervention will report fewer days of hazardous drinking and improved perception of SRV risk cues on the video risk perception measure (primary outcomes) as compared with participants in the HEC condition.

Differences in relevant outcome variables (e.g., number of heavy drinking days, perception of SRV risk cues) will be tested using a 2 (Condition: RPCW vs. HEC) x 4 (Time: baseline, post-treatment, and 3- and 6-month post-treatment) repeated-measures analysis of variance (RM-ANOVA). The primary effects of interest are the intervention condition main effect and the intervention x time interaction. If a significant condition by time interaction is found, it means that (a) change over time in heavy drinking days differs across intervention conditions and (b) the effect of intervention condition on the outcome is different across time. Therefore, a significant intervention condition by time interaction will be explored by computing the conditional effect of time for each intervention condition and (b) the conditional effect of treatment condition at each of the four time points.

Hypothesis b: Participants in the RPCW intervention will report increased knowledge of safe dating practices and protective behavioral (drinking) strategies (secondary outcomes) compared with participants in the HEC condition.

Differences in relevant outcome variables (e.g., safe dating practices, protective behavioral drinking strategies) will be tested using the same 2 (Condition) x 4 (Time) repeated-measures analysis of variance (RM-ANOVA) described above for hypothesis a.

Hypothesis c: Participants in the RPCW intervention will report lower rates of SRV as compared with participants in the HEC condition at 6-month post-intervention follow-up.

Given that SRV has a low base rate of occurrence, we consider this hypothesis exploratory and will conduct a preliminary comparison of the incidence of SRV at 3-months and 6-months post-treatment across the RPCW and HEC conditions using a chi-square test.

Effect sizes will be calculated with all analyses in preparation for a Stage II efficacy trial of the intervention.

17.2 If applicable, provide a power analysis.

NOTE: This may not apply to certain types of studies, including chart/records reviews, survey studies, or observational studies. This question is asked to elicit whether the investigator has an adequate sample size to achieve the study objectives and justify a conclusion.

Response:

Study 2:

The sample size of 96 women (48 women per intervention condition) was selected to provide 80% power to detect at least medium effect sizes in RM-ANOVA. For Hypotheses a and b, power calculations were conducted for a 2 (treatment condition) x 4 (time) RM-ANOVA. We calculated power using the following assumptions (1) a sample size of 48 women in each intervention condition (RPCW, HEC), (2) 4 time points for assessment (baseline, post-intervention, and 3- and 6-months post-intervention), (3) a range of correlation values among repeated assessments ($r = .3$ to $.9$), (4) no violation of the sphericity assumption, (5) $\alpha = .05$, two-tailed, and (6) power = 80%. Based on these assumptions, there is 80% power to detect an intervention condition main effect with medium effect sizes ($f = .20$ to $.28$) and both a time main effect and an intervention condition x time interaction with small to medium effect sizes ($f = .05$ to $.21$). For Hypothesis c, statistical power was estimated for a χ^2 test (1 df) of the number of women who were and were not revictimized post treatment by intervention condition (RPCW, HEC). Assuming (1) a total sample of 96 women, (2) $\alpha = .05$, and (3) 80% power, the chi-square analysis can detect a medium effect ($w = .29$) at 3- and 6-month post-intervention.

17.3 Describe any procedures that will be used for quality control of collected data.

Response:

Study 2:

RPCW/HEC Adherence Scale Development. The proposed study will develop and pilot test RPCW and HEC adherence measures. Adherence refers to the degree to which the interventionist follows the treatment manual guidelines [89, 90]. The RPCW and HEC adherence measures development will be based on our prior experience developing adherence

measures for cognitive-behavioral interventions and HEC conditions [68, 91]. Scale items and written instructions for scoring will be developed during Stage 1a. During Stage 1b, inter-rater reliability of individual items will be calculated by having two raters (PI [name] and Co-I [name]) evaluate the same sessions. Intra-class correlation coefficients (ICCs; [92]) of .70 or better indicate strong agreement and will be considered acceptable for the retention of an item.

Intervention Integrity. Intervention integrity refers to the degree to which the intervention is delivered as intended and will be assessed using several state-of-the art methods [93, 94]. First, both interventions will be manualized. Second, an instructor checklist will be completed following each session to indicate which intervention components were delivered to participants. These are intended to help the Interventionist monitor her own performance and to enhance the supervision process. Third, the clinical supervisors (Drs. [name], [name], and [name]) will conduct weekly supervision with the instructor focused on intervention adherence, competent delivery of the interventions and corrective feedback. Fourth, to facilitate consistency of treatment quality and delivery, all group sessions will be audio-recorded and 25% of the RPCW and HEC intervention sessions will be reviewed and rated for adherence by Drs. [name], [name], and [name] utilizing the RPCW/HEC adherence measures. Problems with adherence and/or competence will require booster training sessions. Controlled trials with more intensive monitoring have yielded stronger outcome data [95].

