Hypothesis 2a: Participants in the RPCW intervention will report fewer days of hazardous drinking and improved perception of SA risk cues on the video risk perception measure (primary outcomes) as compared with participants in the HEC condition.

Hypothesis 2b: Participants in the RPCW intervention will report increased knowledge of safe dating practices and protective behavioral (drinking) strategies (secondary outcomes) compared with participants in the HEC condition.

Hypotheses 2c: Participants in the RPCW intervention will report lower rates of SRV as compared with participants in the HEC condition at 6-month post-intervention follow-up.

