At the beginning of the first in-person session and at the end of the second in-person session, for both the RPCW active intervention and the HEC condition, three standardized instruments will be administered to participants. **Participants will be seated a minimum of 6 feet apart in the group session room and administered these instruments on an individual laptop with earphones to allow them privacy.** These include the Video Vignette Risk Perception Measure (VVRPM) which assesses women's standardized ability to assess sexual assault risk cues. The Adult Faces test from the Diagnostic Analysis of Nonverbal Accuracy 2 (DANVA2) which is used to measure an individual's general ability to sensitivity to perceive nonverbal cues, and the sDERS a measure used to assess state emotion regulation (assessed using a web-based platform as are the other survey measures for the study). All data will be uploaded off of these laptops and saved to the project UB Box at the end of each in-person session.

Outlines for the in-person RPCW and HEC sessions are attached and links to the on-line learning units for both the RPCW and HEC are included for review.

10.2 Describe what data will be collected.

NOTE: For studies with multiple data collection points or long-term follow up, consider the addition of a schedule or table in your response.

Response:

Study 2:

Participants will participate in the intervention over about one week. They will attend two in-person group intervention sessions about one week apart, and complete two on-line units during the intervening week. They will be asked to complete follow-up on-line assessment surveys at 3 months and 6 months post intervention.

The follow-up surveys will be administered online and are included for review.

 *10.3 List any instruments or measurement tools used to collect data (e.g. questionnaire, interview guide, validated instrument, data collection form).*

Include copies of these documents with your submission.

Response:

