Study 2 data collection instruments include: Screening instrument, baseline survey, post-intervention survey with client satisfaction questionnaire, and 3 and 6 month follow up surveys to assess outcomes (i.e., any potential sexual victimization experiences, hazardous drinking/changes in drinking). At the beginning of the first in-person session and at the end of the second in-person session three standardized instruments will be administered via individual laptops. These include the Video Vignette Risk Perception Measure (VVRPM) which assesses women's standardized ability to assess sexual assault risk cues. The Adult Faces test from the Diagnostic Analysis of Nonverbal Accuracy 2 (DANVA2) which is used to measure an individual's general ability to sensitivity to perceive nonverbal cues, and the sDERS a measure used to assess state emotion regulation. A copy of all surveys and measures are attached.

10.4 Describe any source records that will be used to collect data about subjects (e.g. school records, electronic medical records).

Response: None

*10.5 Indicate whether or not **individual** subject results, such as results of investigational diagnostic tests, genetic tests, or incidental findings will be shared with subjects or others (e.g., the subject's primary care physician) and if so, describe how these will be shared.*

Response: N/A

*10.6 Indicate whether or not **study** results will be shared with subjects or others, and if so, describe how these will be shared.*

Response:

Study results will be shared with the scientific community through scientific meetings and publications in peer reviewed journals. If requested, findings will be provided to participants at the end of the study in the aggregate.

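### The video risk-perception measure, a named primary outcome, is scheduled at two occasions but analysed and powered as if measured at four

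*Protocol*

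**What the plan says.** **Outcome.** Protocol 1.2 (Hypothesis 2a) names two primary outcomes: days of hazardous drinking, and "improved perception of SA risk cues on the video risk perception measure (primary outcomes". Protocol 17.1 and the SAP repeat this under Hypothesis a.

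**Schedule.** Protocol 10.1 places three laptop instruments, the VVRPM among them, as follows: "At the beginning of the first in-person session and at the end of the second in-person session, for both the RPCW active intervention" and the control condition. Section 10.3 repeats the two occasions ("at the end of the second in-person session three standardized instruments will be administered via individual laptops"). The sessions are about one week apart. For later contacts, 10.2 says "The follow-up surveys will be administered online and are included for review", and 10.3 describes "3 and 6 month follow up surveys to assess outcomes (i.e., any potential sexual victimization experiences, hazardous drinking/changes in drinking". Section 11.2 gives each follow-up contact 15 to 20 minutes and says that the two group sessions are the only in-person ones. No section places the VVRPM at 3 or 6 months.

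**Analysis.** Protocol 17.1 and the SAP (Data Analyses, Hypothesis a) give one model for the primary outcomes: "e.g., number of heavy drinking days, perception of SRV risk cues) will be tested using a 2 (Condition: RPCW vs. HEC) x 4", the four levels being baseline, post-treatment, 3 months and 6 months. A significant interaction is to be followed by "the conditional effect of treatment condition at each of the four time points". On missing data: "To adjust for any missing assessments, we will use multiple imputation procedures", with no more than 5% of data expected to be missing.

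**Power.** Protocol 17.2 and the SAP (Power) use four time points for Hypotheses a and b. They report detectable effects of f = .20 to .28 (condition) and f = .05 to .21 (condition x time).

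**The concern.** A four-level time factor needs data at four times. As scheduled, the VVRPM has data at two. The model written for one of the two primary outcomes would then not be estimable, and whoever analyses the data would have to choose a replacement after the fact. The candidate replacements differ widely in what they can detect.

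The time frame of the claim is also at stake. Hypothesis 2a sets no time point, so an immediate post-intervention result does address it. But a reader of the analysis section would expect evidence on risk perception at 3 and 6 months. The plan also says that effect sizes will feed a Stage II trial. On the written schedule, the VVRPM effect size would be an immediate post-training effect and should not be carried forward as a 6-month one.

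**Working it through.** **Step 1. Occasions set side by side.**

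| Time level in the 2 x 4 model | VVRPM scheduled in 10.1 / 10.3? |
|---|---|
| Baseline | Yes, start of session 1 |
| Post-treatment | Yes, close of session 2 |
| 3 months | Not scheduled |
| 6 months | Not scheduled |

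Two of four levels (2/4 = 50%) have no scheduled data in either arm, against an expected maximum of 5% missing. Multiple imputation borrows from observed values. With none at a wave, nothing in the trial identifies that wave's distribution.

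**Step 2. Reproduce the stated power.** Inputs from 17.2: N = 96 (48 per arm), alpha .05 two-sided, 80% power, r = .3 to .9, sphericity. The noncentrality needed on (1, 94) df is 8.012.

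Condition main effect: f = sqrt(lambda x (1 + (m-1)r) / (N x m)).
- m = 4, r = .3: sqrt(8.012 x 1.9 / 384) = .199
- m = 4, r = .9: sqrt(8.012 x 3.7 / 384) = .278

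This matches the stated .20 to .28. For the interaction with m = 4 (3 df, noncentral F), f is .142 at r = .3 and .054 at r = .9. The lower end matches the stated .05. The stated upper end of .21 does not reproduce under sphericity.

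**Step 3. Two occasions (m = 2), r = .3/.5/.7/.9.**
- Main effect: sqrt(8.012 x (1 + r) / 192) = .233/.250/.266/.282
- Interaction: sqrt(8.012 x (1 - r) / 192) = .171/.144/.112/.065

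These fall within the stated ranges, or round into them. Against the recomputed four-occasion interaction (.142 to .054), the two-occasion values are about 20% larger (.171/.142 = 1.20).

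**Step 4. Compare the two-occasion tests on one scale.** Let d be the standardised difference in the session-2 score. Assume equal expected baselines, equal pre and post variances and no clustering. Put h = 1/48 + 1/48 = .0417. The ANCOVA noncentrality on (1, 93) df is 8.014.

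- ANCOVA: d = sqrt(8.014 x (1 - r^2) x h)
- 2 x 2 interaction (change score): d = sqrt(8.012 x 2(1 - r) x h)
- 2 x 2 condition main effect: d = sqrt(8.012 x 4 x h x (1 + r)/2). The factor 4 arises because averaging with baseline halves the difference.

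| Test | r = .3 | r = .5 | r = .7 | r = .9 |
|---|---|---|---|---|
| ANCOVA | 0.55 | 0.50 | 0.41 | 0.25 |
| 2 x 2 interaction | 0.68 | 0.58 | 0.45 | 0.26 |
| 2 x 2 main effect | 0.93 | 1.00 | 1.07 | 1.13 |

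The ratio of change-score to ANCOVA variance is 2/(1 + r) = 1.54/1.33/1.18/1.05. A simulation of 6,000 runs at r = .5 and d = .50 gave power of 80% (ANCOVA), 68% (change score) and 29% (main effect). If 5% of women had no usable session-2 score (N = 91, 46 and 45), ANCOVA would need d = 0.57/0.51/0.42/0.26.

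**The case against.** **The deciding documents are unseen.** The follow-up surveys are attachments and could contain the VVRPM. This stands, so the finding is a contradiction in the text and not proof that the data were never to be collected. If the surveys do contain it, 10.1 and 10.3 are incomplete for a primary outcome and still need correcting.

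**Some supporting evidence is weak.** The description of the follow-up surveys in 10.3 also omits the Hypothesis b outcomes, so it may not be exhaustive. No document gives the VVRPM's duration, so a 15-to-20-minute contact proves nothing. Both points are fair. The weight rests on the two statements tying the measure to the two sessions, on study laptops in the session room.

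**The fallback is obvious.** Dropping two levels leaves a 2 x 2 RM-ANOVA with the same two effects of interest, in a pilot whose aims include feasibility and acceptability. That would remove the contradiction, but the plan does not say it. The condition main effect, listed as of primary interest, would then be the weakest of the available tests.

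**ANCOVA is a preference.** In part this is so: the mismatch exists whichever test is chosen, and at r = .9 ANCOVA and the change score are almost equal (0.252 and 0.258). ANCOVA still needs a smaller effect at every r and uses only data already scheduled.

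**The power comparison is loose.** The two-occasion interaction sits inside a stated range whose upper end does not reproduce. Compared like for like, an interaction f detectable with 80% power at four occasions has 64% power at two. This is accepted. The N = 91 figures are likewise illustrative, since the plan's 5% covers all waves and is to be imputed.

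**Conclusion.** The concern holds. As written, the schedule and the model for a named primary outcome contradict each other. On that schedule, the 3-df interaction and the 3- and 6-month contrasts cannot be computed for the VVRPM, and imputation does not rescue them. The defect lies in the model and in the time frame of the claim. It is not a case for changing the sample size, and it does not touch drinking days, which the follow-up surveys are said to cover.

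Its practical size is the spread between the analyses that might be substituted: at r = .5, d = 0.50, 0.58 or 1.00, depending on the test. These figures assume equal variances, equal expected baselines, 96 women analysed and no allowance for group clustering. Confidence is moderate because the attached surveys could not be read.

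**What to change.** Check the 3- and 6-month surveys, then reconcile Protocol 10.1 and 10.3 with Protocol 17.1 and 17.2 and with the SAP.

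1. **If the surveys contain the VVRPM:** say so in 10.1 and 10.3 and keep the 2 x 4 model.
2. **If they do not:** in 17.1 and the SAP, take the VVRPM out of the 2 x 4 model. Prespecify ANCOVA of the session-2 score on condition, adjusted for the session-1 score. State that the risk-perception conclusion applies immediately post-intervention. In 17.2 and the SAP's Power section, give this outcome its own detectable effect: d about 0.55 (r = .3) to 0.25 (r = .9) with 96 women, or 0.57 to 0.26 with 91, before any allowance for group clustering.

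Both are wording changes with no new data collection. The price of the second is that there is no risk-perception result at 3 or 6 months. If four occasions were intended and the surveys lack the measure, adding it would also reconcile the text. That is new data collection at two contacts, and 10.1, 10.3 and the contact length in 11.2 would have to change.

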10.0 Procedures Involved

*10.1 Provide a description of **all research procedures or activities** being performed and when they are performed once a subject is screened and determined to be eligible. Provide as much detail as possible.*

NOTE: This should serve as a blueprint for your study and include enough detail so that another investigator could pick up your protocol and replicate the research. For studies that have multiple or complex visits or procedures, consider the addition of a schedule of events table in in your response.

Response:

Study 2:

During the Stage 1b Randomized Controlled Trial of the active intervention, the first group session will focus on viewing each of 4 cue recognition training videos and the Interventionist will lead a discussion intended to highlight the risk cues in each of the videos. After the session, links and passwords will be sent via email to each participant for the online safe dating and safe drinking learning modules and participants will be asked to complete them prior to the second group session, which will take place about one week after the first session. This second group session will elicit feedback on the dating and drinking learning modules (e.g., length, ease of use, engagement, interest). The training videos will be viewed again individually and participants will engage in behavioral skills rehearsal of appropriate responses in paired role plays with feedback from the PI and Interventionist. During the behavioral rehearsal segment, the PI or Interventionist will engage the group in a discussion of emotional barriers to engaging in appropriate dating and drinking safety behaviors (e.g., "I feel bad for the guy", "He might get really mad, "I might miss out on being with a great guy") and strategies for overcoming these barriers. Adaptive emotion regulation strategies will include cognitive reappraisal, distress tolerance, mindfulness of current emotions, acceptance, and problem solving. Immediately following this session, the post-intervention measures, including feedback on the intervention content and process, will be completed. Following the in-person RPCW sessions, a debriefing will occur to ensure that women have an opportunity to discuss any emotional discomfort or distress with the interventionist. Women will receive \$30 for completion of the post-intervention measures.

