Health education control (HEC). The two in-person sessions and two online units of the HEC condition will impart health information that is relevant and engaging for college women but does not directly address heavy drinking or SA risk. *Thus, the proposed HEC condition is a time and attention control intended to control for nonspecific intervention factors related to health behavior change.* This 4-session active control condition will begin with information regarding the importance of good health and its association to academic, relationship and vocational success. This will be followed by a discussion of health concerns from group members. Following the first group session, links and passwords will be emailed to

participants for the two online learning modules: (1) good nutrition simplified and (2) developing an exercise plan. These two modules are similar in format to the drinking and dating safety modules provided in the RPCW. The second group session will, importantly, elicit feedback regarding the relevance of the content and ensure the learning modules are being presented in an engaging format. In addition, at this session, we will present information on strategies for good sleep derived from a popular, empirically-validated cognitive-behavioral program to manage insomnia [88] and elicit similar feedback on this material. To ensure that HEC participants receive SA risk reduction and HD reduction information, they will have the opportunity to receive the RPCW intervention following the 6-month follow-up assessment, if they choose to do so.

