25.0 Compensation for Participation

25.1 *Describe the amount and timing of any compensation to subjects, including monetary, course credit, or gift card compensation.*

Response:

Study 2: Participants will be remunerated \$30 for the baseline survey at the first group intervention session, \$30 for the post intervention survey, \$40 for the 3 month follow-up survey, and \$50 for the 6 month follow-up survey.

N/A: This study is not enrolling subjects, or is limited to records review procedures only. This section does not apply.

N/A: There is no compensation for participation. This section does not apply.

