26.0 Consent Process

26.1 *Indicate whether you will be obtaining consent.*

NOTE: This does not refer to consent documentation, but rather whether you will be obtaining permission from subjects to participate in a research study. Consent documentation is addressed in Section 27.0.

Yes *(If yes, Provide responses to each question in this Section)*

No *(If no, Skip to Section 27.0)*

26.2 *Describe where the consent process will take place. Include steps to maximize subjects' privacy.*

Response:

Study 2: Consent will occur prior to completing the initial baseline survey before the first group intervention session. Group sessions will be small, limited to 8 women. Every effort will be made to include women who do not know each other in each group session. In addition, if a woman has a concern or question about consent she will be given the opportunity to meet with the PI or Project coordinator by telephone to answer questions and provide individual consent.

26.3 Describe how you will ensure that subjects are provided with a sufficient period of time to consider taking part in the research study.

NOTE: It is always a requirement that a prospective subject is given sufficient time to have their questions answered and consider their participation. See “SOP: Informed Consent Process for Research (HRP-090)” Sections 5.5 and 5.6.

Response:

Study 2: Each woman will be emailed a link to the online consent form and provided with time to read the consent document, the project coordinator or one of the study team members will then provide a summary of the main points of the document and provide time for all questions to be answered. Once the participant has had time to ask any questions, she will be asked to initial and sign the online consent document exit the document. This will send a message to the study email indicating that the consent document has been signed and saved in the Qualtrics secure data server.

26.4 Describe any process to ensure ongoing consent, defined as a subject’s willingness to continue participation for the duration of the research study.

Response:

Study 2: Prior to each study activity, participants will be verbally asked to indicate their willingness to continue to participate in the study.

26.5 Indicate whether you will be following “SOP: Informed Consent Process for Research (HRP-090).” If not, or if there are any exceptions or additional details to what is covered in the SOP, describe:

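### Both arms are delivered in groups of up to 8 women, but the tests and the power statement treat all 96 women as independent; if group contact makes women alike, the true error rate exceeds 5%

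*Protocol*

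**What the plan says.** Protocol 1.1 randomises individual women to RPCW or HEC. Neither document says how women are then placed in session groups.

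Delivery is in groups. Protocol 10.2: "They will attend two in-person group intervention sessions about one week apart, and complete two on-line units during the intervening week". Protocol 26.2: "Group sessions will be small, limited to 8 women". In RPCW (10.1) there is led discussion, and "participants will engage in behavioral skills rehearsal of appropriate responses in paired role plays with feedback from the PI and Interventionist". In HEC (10.1) the opening material is on good health: "This will be followed by a discussion of health concerns from group members". Whether the same women stay together for both sessions is not stated.

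Baseline comes before group work. Protocol 26.2: "Consent will occur prior to completing the initial baseline survey before the first group intervention session". Protocol 25.1 pays "for the baseline survey at the first group intervention session". Protocol 26.2 adds: "Every effort will be made to include women who do not know each other in each group session".

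Under 17.1 and the SAP, outcomes for Hypothesis a "will be tested using a 2 (Condition: RPCW vs. HEC) x 4 (Time: baseline, post-treatment, and 3- and 6-month post-treatment" in a repeated-measures ANOVA, with the condition main effect and condition x time as the effects of interest. Hypothesis b uses the same model, and Hypothesis c a chi-square test. The six power assumptions in 17.2 and the SAP include no session group, ICC or design effect. The only ICC in either document, in 17.3, concerns agreement between raters of adherence items.

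**The concern.** Women who share an interventionist, a discussion and role-play partners may end up more alike than women in different groups. With full groups there are only 12 of them, 6 per arm, so a chance difference between a few groups can look like a difference between arms. An analysis that counts 96 independent women understates the standard error of the arm comparison.

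The plan's product is effect sizes for a Stage II trial (17.1). Clustering does not bias the between-arm estimate, but it makes the interval around it too narrow and the p-value too small. Group membership that is not recorded as sessions happen may be hard to reconstruct, and without it the ICC cannot be estimated.

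**Working it through.** **Inputs from the documents.** N = 96, 48 per arm; two-tailed alpha .05; 80% power; m = 4 time points; r = .3 to .9; sphericity (17.2 and SAP, Power). Group size at most 8 (26.2), so full groups give 48/8 = 6 per arm.

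**Assumed.** ICC = .01, .05 or .10, meaning the share of the variance of the tested quantity that lies between groups. Because 8 is a cap, groups of 4 are shown as well.

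**1. The plan's own figures.**
- Condition main effect: noncentral F(1, 94) with λ = f²·N·m/(1 + (m − 1)r). 80% power needs λ = 8.01. At r = .3, f = √(8.01 × 1.9/384) = .199. At r = .9, f = √(8.01 × 3.7/384) = .278. Stated: .20 to .28.
- Chi-square: λ = N·w². 80% power needs λ = 7.85, so w = √(7.85/96) = .286. Stated: .29, which has 81% power.

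Both reproduce with 96 independent women, that is, at ICC 0.

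**2. Error of a 1-df arm comparison that ignores groups** (arm difference at a post-baseline visit, or in change from baseline). Design effect DE = 1 + (8 − 1)·ICC. Approximate error = 2[1 − Φ(1.96/√DE)], which is .058/.092/.133 at ICC .01/.05/.10. Simulation (40,000 trials per cell) gives .059/.094/.134. A test on group means gives .049 to .050.

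**3. Power at the effect stated to have 80%.** A test that holds 5% error has λ = 8.01/DE. The uncorrected test is simulated.

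| ICC | DE | 96/DE | Error, uncorrected | Power, uncorrected | Power at true 5%, 94 df | Power at true 5%, 10 df |
|---|---|---|---|---|---|---|
| 0 | 1.00 | 96 | 5% | 80% | 80% | 72% |
| .01 | 1.07 | 90 | 6% | 79% | 77% | 69% |
| .05 | 1.35 | 71 | 9% | 76–77% | 67% | 59% |
| .10 | 1.70 | 56 | 13% | 75% | 57% | 50% |

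The 94-df column shows variance inflation alone. The 10-df column is a comparison of 12 group means. Groups of 4 at ICC .05: DE = 1 + 3 × .05 = 1.15, error about 7%, power 74% (71% on 22 df).

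**4. Chi-square.** With an assumed 20% SRV rate and groups of 8, simulated error is .060/.094/.136 at ICC .01/.05/.10. At w = .29, power at a true 5% level is 81% at ICC 0, then 78/69/59%.

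**5. Condition x time, F(3, 282), simulated.**
- Group effect equal at all four visits: .050 (ICC .05, r = .6) and .048 (ICC .10, r = .3). It cancels.
- Group effect on the three post-baseline visits only, ICC defined on change from baseline, .01/.05/.10: .052/.077/.107 at r = .3 and .052/.069/.107 at r = .9.

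**6. Re-mixed groups.** If half the group variance comes from each session's group, the uncorrected 1-df test still rejects .091/.134 at ICC .05/.10. A test on session-1 group means alone then rejects .063/.078. So the problem does not depend on fixed membership, but the remedy does.

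**The case against.** The strongest reply is that the ICC may be small. In-person contact is two sessions of at most 1.5 hours (11.2), the modules are done privately on-line (12.1), speaking in the group is optional (16.1), delivery is manualised (17.3), and women who know each other are to be kept apart where possible (26.2). At ICC .01 the error is about 6%, which is slight. Groups smaller than 8 reduce the effect further. All of this stands, and it is why no size is claimed. It does not answer the omission, since the plan neither states nor checks the value on which its 5% and 80% depend.

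It is also fair that this is a Stage 1b pilot, that Hypothesis c is declared exploratory, and that what goes forward is effect sizes, which are unbiased. That limits the severity, but intervals that are too narrow would still go forward with them.

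Three stronger readings are tempting and should be resisted:
- A reader might infer that the planned test has both 9% error and 67% power at ICC .05. No single test has both. The uncorrected test keeps about 76–77% power at 9% error; 67% belongs to a test corrected to 5%.
- A reader might infer that condition x time is necessarily inflated. A group effect that is constant over visits leaves it at 5%. Inflation needs an effect that starts or changes after baseline. That is plausible, because baseline precedes group contact and groups are meant to be made up of strangers, but the documents do not establish it.
- A reader might infer that the results would be invalid or the estimate biased. Neither follows; the fault lies in the stated precision.

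**Conclusion.** The omission is certain: treatment is delivered in groups in both arms, and no test or power figure allows for it. The consequence is conditional on a positive within-group correlation that the documents do not give. Under the assumed range and full groups of 8, a nominal 95% interval for a 1-df arm comparison covers about 94/91/87% (100% less the error in step 2). The stated 80% power at a true 5% level holds only at ICC 0. Should-fix: high confidence in the omission, none claimed for its size.

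**What to change.** 1. Record each woman's assigned group at each session, and state whether membership is fixed across the two sessions.
2. For Hypotheses a and b, pre-specify a group-adjusted analysis: a mixed model with a random group effect on the post-baseline visits and small-sample df or, if groups are fixed, a comparison of group means of change from baseline on (groups − 2) df. If groups are re-mixed, the model must carry both session groups. Include group in the imputation model.
3. For Hypothesis c, keep the chi-square test as exploratory and add a comparison of group-level SRV proportions as a sensitivity analysis.
4. In 17.2 and the SAP, state that 80% power assumes ICC 0, and give the power of the group-adjusted test over ICC .01 to .10 for the planned group size. Report the observed ICC with its interval, labelled imprecise: with 12 groups of 8 and an estimate of .05, the 95% interval is about −.05 to .30.

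Cost: a group variable per session and revised wording, with no extra participants. The price is fewer df and a larger detectable effect. On 10 df, 80% power needs λ = 9.67, so with groups of 8 at ICC .05 the detectable effect grows by √(9.67 × 1.35/8.01) = 1.28, about 28%. At ICC 0 it grows by √(9.67/8.01) = 1.10, about 10%, from the df alone.
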